## 1 Introduction

### 1.1 Scope of document

The RAP documents contain detailed information to aid the production of Statistics & Programming input into the Clinical Study Report (CSR) for trial “**CDFV890D12201**”.

The Statistical analysis plan (SAP) describes the implementation of the statistical analysis planned in the protocol to be reported in the CSR. The data presentation and analyses for the DMC are not part of this analysis plan.

### 1.2 Study reference documentation

This SAP Amendment 1 is based on the protocol amendment 1 for study CDFV890D12201 dated 22-Jun-20.

### 1.3 Study objectives

**Table 1-1 Study objectives**

Objective(s)	Endpoint(s)
Primary Objective(s) 
 
To evaluate the effect of DFV890 in addition to SoC, compared with SoC alone, on the Acute Physiology and Chronic Health Evaluation II (APACHE II) score
 
	Endpoint(s) for primary objective(s) 
 
APACHE II severity of disease score on Day 15 or on day of discharge (whichever is earlier) with worst case imputation for death
 

Secondary Objective(s) 
 
To evaluate the effect of DFV890 in addition to SoC, compared with SoC alone, on inflammatory status
 
To evaluate the effect of DFV890 in addition to SoC, compared with SoC alone, on clinical status
 
	Endpoint(s) for secondary objective(s) 
 
Serum C-reactive protein (CRP) levels
 
 Endpoints based on the 9-point ordinal scale: 
 
Survival without the need for invasive mechanical ventilation at Days 15 and 29
 
At least one level improvement in clinical status at Days 15 and 29
 
Clinical status over time
 

 
To evaluate the safety of DFV890 in addition to SoC, compared with SoC alone
 
	
 
Number of participants with Adverse Events (AE), Serious Adverse Events (SAE), clinically significant changes in laboratory measures, and vital signs
 

Commercially Confidential Information

[figure not shown]
#### **1.4 Study design and treatment**

This is a Phase 2, randomized, controlled, open label multi-center study to assess the efficacy and safety of DFV890 for the treatment of SARS-CoV-2 infected patients with COVID-19 pneumonia and impaired respiratory function ([Figure 1-1](#)).

Written informed consent will be obtained from participants before any study related assessments or procedures are performed. Thereafter, medications and eligibility criteria will be reviewed by study personnel. All participants signing informed consent must be registered by study staff in the Interactive Response Technology (IRT).

Assessments during the study will occur per the schedule of study assessments as described in the protocol.

**Figure 1-1 Study design**

\*If participant discharged from hospital prior to Day 15, investigational treatment should be taken at home to complete the 14-day treatment period.

The study consists of four parts:

1. **Screening / Baseline visit** (Day -1 to 1): lasts up to a maximum of 24 hours and comprises a screening / baseline assessment. This visit will be used to confirm that the study inclusion and exclusion criteria are met and serves as baseline assessment prior to randomization.

Commercially Confidential Information

Baseline blood tests will be performed in all participants; those who screen fail because of study inclusion / exclusion criteria (e.g., serum CRP, liver function tests), will not undergo randomization.

2. **Treatment period** (Day 1-15): Participants in the investigational treatment arm will receive DFV890 + CCI orally or via a nasogastric feeding tube administered for a total of 14 days + CCI in addition to SoC. Study drug will be supplied in tablet form which can be crushed, allowing for both oral and nasogastric administration. Participants in the control arm will receive SoC alone.

Participants will be randomized as soon as possible, but within a maximum of 24 hours after screening in a 1:1 ratio to receive either DFV890 in addition to SoC or SoC alone.

Commercially Confidential Information

Study assessments will be conducted every 2 days for hospitalized participants.

The End of Treatment (EOT) visit will take place on Day 15. If participants are discharged from the hospital prior to Day 15, assessments on the day of discharge should be performed according to the schedule listed under Day 15; participants will continue to take the investigational treatment at home to complete the 14-day treatment period and the participants should return to the site for the Day 15/EOT assessment (all other visits between discharge and Day 15 can be omitted). If a hospital visit is not possible at Day 15, then home nursing services may be used to support this last visit where these are available in

accordance with local guidelines and should include all possible assessments (e.g., oxygen saturation with portable monitors).

3. **Follow-up** (Day 16-29): After completion of the 14 day- treatment period, participants will be observed until Day 29 or discharged from hospital, whichever is sooner. Study assessments to be conducted every 2 days for hospitalized participants. If participants are discharged from hospital prior to Day 29, a study visit conducted by telephone will occur on Day 29 (all other visits between discharge and Day 29 can be omitted).
4. **30-day safety follow-up assessment** (Day 45): A follow-up visit for safety will be conducted by telephone.

## 2 **First interpretable results (FIR)**

Commercially Confidential Information

## 3 **Interim analyses**

Commercially Confidential Information

## 4 **Statistical methods: Analysis sets**

For all analysis sets, participants will be analyzed according to the study treatment(s) randomized.

The Safety analysis set will include all randomized participants.

Commercially Confidential Information

The PD analysis set will include all randomized participants with no protocol deviations with relevant impact on PD data.

The analysis sets and protocol deviation codes are related as follows:

**Table 4-1 Protocol deviation codes and analysis sets**

Category Deviation code	Text description of protocol deviation	Additional condition	Data exclusion
Subjects are excluded from safety analysis in case of these conditions:			Exclude subject from safety analysis set
INCL02	Informed consent form not obtained		Yes

Commercially Confidential Information

Subjects are excluded from PD analysis in case of these conditions:			Exclude subject from PD analysis set
TRT02	Study treatment dose adjustments and/or interruptions	Study treatment dose interruptions resulting in exposure of less than 6 consecutive doses	Yes
TRT02	Study treatment dose adjustments and/or interruptions	Study treatment dose interruptions resulting in exposure of at least 6 consecutive doses	No
INCL06	Patient enrolled but APACHE II score is less than 10 at Screening Visit		Yes
INCL03	Patient randomized but no confirmed coronavirus (SARS-CoV)-2 infection		Yes
INCL02	Informed consent form not obtained		Yes

If updates to this table are needed, an amendment to the SAP needs to be implemented prior to DBL.

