## **6.2 Secondary objectives**

### **6.2.1 Variables**

The following variables and corresponding objectives are classified as secondary pharmacodynamic endpoints and will be evaluated for their effect of DFV890 in addition to SoC compared with SoC alone:

- On inflammatory status: Serum C-reactive protein (CRP) levels

- On clinical status: Endpoints based on the 9-point ordinal scale:
  - Survival without the need for invasive mechanical ventilation at Days 15 and 29: defined by a 9-point ordinal scale score of  $< 6$  points at all time points
  - At least one level improvement in clinical status at Days 15 and 29: defined as improvement of  $\geq 1$  in the 9-point ordinal scale score of the screening value – Day 15 or Day 29 score respectively.
  - Clinical status over time

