### **6.2.3 Statistical model, assumptions and hypotheses**

#### **CRP**

CRP levels are assumed to follow a log-normal distribution. Thus the log-transformed CRP data will be analyzed by fitting an MMRM model. Treatment, visit and their interaction as well as the three stratification factors will be included as fixed factors and log-transformed baseline CRP as a covariate. Interactions between visit and each of the terms in the model will also be included. To model the dependency of observations an unstructured variance-covariance matrix will be fitted.

The analysis will be performed on the PD analysis set. All available values at all scheduled visits (excluding discharge or early discharge visits) up to Day 29 will be included in this analysis. The back-transformed geometric means for both treatment groups as well as the geometric mean ratios (DFV890 in addition to SoC vs SoC alone) will be reported together with 90% confidence intervals (CIs) for each visit. The 1-sided p-value for the overall treatment factor will be reported.

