### **7.2.2 Treatment**

The duration of exposure to DFV890 in days will be summarized as well as the number and percentage of participants with treatment compliance of <80% and ≥80% respectively.

Concomitant medications and significant non-drug therapies prior to and after the start of the study treatment will be listed and summarized according to the Anatomical Therapeutic Chemical (ATC) classification system by treatment group. For corticosteroids ATC-Subclasses will be added. Convalescent plasma treatment will included in the anti-viral treatment presentations.

For any of the below mentioned three treatment categories, if it started prior to randomization and continued during the study, it will be reported under baseline as well as part of SoC during study participation.

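### The 6-dose exclusion in the PD analysis set can act only on the DFV890 arm, so the CRP model compares a selected treated group with an unselected control group

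*SAP*

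**What the plan says.** Section 4 defines the set by deviations: "The PD analysis set will include all randomized participants with no protocol deviations with relevant impact on PD data". Table 4-1 lists which deviations count. Under TRT02 a participant is excluded for "Study treatment dose interruptions resulting in exposure of" less than 6 consecutive doses and kept with 6 or more. The other visible PD exclusions are absence of consent, unconfirmed SARS-CoV-2 infection and a screening APACHE II score below 10.

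Section 1.4 describes a "randomized, controlled, open label multi-center study", with allocation "in a 1:1 ratio to receive either DFV890 in addition to SoC or SoC alone". It adds: "Participants in the control arm will receive SoC alone". Section 7.2.2 plans an exposure summary for the investigational drug only: "The duration of exposure to DFV890 in days will be summarized".

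For CRP, Section 6.2.3 says: "The analysis will be performed on the PD analysis set". It reports geometric mean ratios with 90% confidence intervals by visit and a 1-sided p-value for treatment. The primary endpoint is handled differently. Section 6.1.3 analyses it on the Safety analysis set, and Section 6.1.1 applies a treatment policy strategy to treatment discontinuation.

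**The concern.** TRT02 is the only visible PD exclusion that depends on what happens after randomisation and that only one arm can trigger. The consent, infection and screening-score exclusions concern status at entry and can occur in either arm.

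A DFV890 participant with too few consecutive doses leaves the CRP analysis. The comparable control participant, who would have had the same interruption if allocated to DFV890, cannot be identified and stays in. If interruption is related to CRP, the two groups differ in CRP even when the drug does nothing.

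What is at stake is the CRP result. Among the secondary efficacy endpoints it is the only one for which the visible text gives a model and a p-value.

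**Working it through.** **Tracing the rule.**
1. TRT02 counts study-drug doses (Table 4-1).
2. Only the DFV890 arm has such doses: the trial is open label, control is standard of care alone (Section 1.4), and exposure is summarised for DFV890 only (Section 7.2.2).
3. The CRP model uses the PD set (Section 6.2.3). The visible text of Section 6.2 contains no CRP model on all randomised participants and no matching exclusion for control.

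The DFV890 group is therefore selected on a post-randomisation event and the control group is not.

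**Size.** The SAP gives no figure to reproduce: the visible text has no sample size, CRP standard deviation or expected exclusion rate. All inputs below are assumptions.

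Let f be the share of the DFV890 arm removed and r the ratio of geometric mean CRP in those removed to that in those kept. With no drug effect, randomisation makes the control mean of log CRP equal to that of the whole DFV890 arm, which lies f × ln r above the mean of those kept. Hence

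spurious GMR = exp(−f × ln r).

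| f | r | f × ln r | GMR |
|---|---|---|---|
| 0.03 | 2 | 0.021 | 0.979 |
| 0.05 | 3 | 0.055 | 0.947 |
| 0.10 | 3 | 0.110 | 0.896 |
| 0.10 | 5 | 0.161 | 0.851 |

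With r = 1 the GMR is 1.00. With r below 1 the bias reverses: f = 0.10 and r = 0.5 give exp(0.069) = 1.07. These are unadjusted figures; the planned model also adjusts for baseline CRP.

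**Effect on the p-value.** Suppose a share q is removed and those removed lie m standard deviations above their arm's mean log CRP. Then

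bias = −q × m × SD / (1 − q), SE = SD × √(1/(n(1 − q)) + 1/n),

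and the rejection rate is Φ(|bias|/SE − 1.2816). Assume SD = 1.0 and n = 50 to 100 per arm. The one-sided 10% level is borrowed from the primary endpoint, since the SAP sets none for CRP.

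Example with q = 0.05, m = 1, n = 50: bias = −0.05/0.95 = −0.053; SE = √(1/47.5 + 1/50) = 0.203; rate = Φ(0.260 − 1.282) = 0.153.

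| q | m = 0.5 to 1.0: GMR | Rejection rate with no drug effect |
|---|---|---|
| 2% | 0.99 to 0.98 | 10.9% to 12.8% |
| 5% | 0.97 to 0.95 | 12.5% to 18.0% |
| 10% | 0.95 to 0.89 | 15.6% to 30.3% |

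With m = 0, or with nobody removed, the bias is zero and the rate stays at 10%.

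**The case against.** The best defence is that a pre-specified PD set with a minimum exposure asks a pharmacological question about a biomarker, and that secondary endpoints need not share the primary estimand. This does not rescue the comparison. The objective in Table 1-1 is the effect of DFV890 plus standard of care against standard of care alone, with no restriction to adequately exposed participants. Even for an effect in exposed participants, an unselected control arm is the wrong comparator unless interruption is unrelated to CRP.

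Several other objections stand and limit the point:

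- **What triggers TRT02.** A reader might infer that everyone who stops DFV890 for an adverse event, deterioration or intolerance is removed. Table 4-1 does not say so. The row speaks of dose adjustments and interruptions, while Sections 6.1.1 and 6.1.5 use discontinuation for stopping. Whether permanent stopping, early death or never starting is coded TRT02 is not stated.
- **Direction.** A reader might infer that the bias must favour DFV890. That needs those removed to have higher CRP, which the SAP neither states nor lets one check.
- **Size.** The model adjusts for log baseline CRP and the stratification factors, each interacting with visit. If those removed were already sicker at entry, part of r is absorbed and the unadjusted figures are too large. Differences that arise after baseline are not absorbed. Dosing frequency is blacked out, so a plausible f cannot be judged.
- **Weight.** The CRP p-value is only reported. No decision rule depends on it.

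**Conclusion.** The point holds for CRP. The PD set applies a post-randomisation exclusion that only the DFV890 arm can meet, and the only visible CRP model uses that set. Bias in the geometric mean ratio and its p-value is possible whenever early interruption is related to CRP. Its size and direction cannot be fixed from the SAP. The range of 0.98 to 0.85 rests on an assumed 3-10% removed, an assumed CRP ratio of 2-5 and no baseline adjustment.

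Three wider readings are not supported:

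- The primary APACHE II analysis is not affected, because it uses the Safety analysis set.
- The 9-point-scale endpoints cannot be said to inherit the exclusion. Section 6.2.1 says the secondary endpoints "are classified as secondary pharmacodynamic endpoints", but the primary endpoint also sits in the PD chapter and is analysed on the Safety set, so that label does not assign the PD set. Section 6.2.3 names the PD set for CRP only, and the visible 9-point outputs are descriptive or graphical.
- Randomisation is not abandoned altogether. Participants are still analysed by randomised arm; the fault is that one arm is selected and the other is not.

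This should be fixed, but it is not critical to the trial's main conclusion.

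**What to change.** In Section 6.2.3, name the Safety analysis set (all randomised participants, less anyone without informed consent under Table 4-1) as the main population for the CRP model. Participants with interrupted dosing then stay in, in line with the primary endpoint's treatment policy strategy. Keep the same model on the PD analysis set as a supportive analysis, labelled as such.

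With nobody removed by the one-arm rule, the selection bias in the illustration is zero and the rejection rate returns to 10%.

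The cost is an SAP amendment before database lock, a changed population flag and one extra model run, with no new data. The main CRP estimate will be somewhat diluted by participants with little exposure, and it will also include the participants now excluded for unconfirmed infection or a low screening score. The supportive PD-set run still shows the result in the more exposed group.

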#### 4.1 Baseline

The baseline value is defined as the last assessment performed on or prior to randomization.

## 4.2 Unscheduled visits

Data collected at unscheduled visits will be used to replace missing values if a Last observation carried forward (LOCF) approach is applied within the allowed LOCF period of maximum 4 days (i.e. for the mortality scores APACHE II, Commercially Confidential Information as described in [Sections 6.1.6](#) and [Section 6.3.1](#)).

In addition for the screening/baseline visit unscheduled assessments within 24 hours prior to signing the Informed Consent Form (ICF) can be used.

For other type of analyses and other visits no unscheduled visits data will be considered.

Commercially Confidential Information

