### Missing data

For the clinical status 9-point ordinal scale missing values will be handled as follows:

- For participants who died prior to Day 29: The score for death will be imputed for all visits following the death up to and including Day 29.
- For all other participants: LOCF will be applied up to and including Day 29. Following discharge or early discharge LOCF will be applied to all intermediate visits. In case the value reported for the (early) discharge visit does not reflect that the patient is ambulatory from now on (i.e. score  $\geq 3$ ), it will be set to the highest ambulatory score i.e. a value of 2 starting from the next scheduled visit.

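### Ventilator-free survival is defined over all time points, but unscheduled 9-point scores are excluded, so a survived intubation that starts and ends between two scheduled scores counts as a success

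*SAP*

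**What the plan says.** The endpoint is set out in SAP 6.2.1. A participant survives without invasive ventilation if the 9-point score is below 6 "points at all time points". In SAP 10.6, 6 and 7 are the two ventilated states and 8 is death. SAP 6.2.2 counts responders cumulatively up to Day 15 and up to Day 29 and gives the difference in rates. SAP 6.2.3 specifies no model or test for this endpoint.

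On unscheduled data, SAP 4.2 states: "Data collected at unscheduled visits will be used to replace missing values if a Last observation carried forward (LOCF) approach is applied", within at most 4 days and for the mortality scores, with references to 6.1.6 and 6.3.1. It adds an allowance for baseline and then closes the list: "For other type of analyses and other visits no unscheduled visits data will be considered".

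On missing ordinal scores (SAP 6.2.1, Missing data):
- Deaths: "The score for death will be imputed for all visits following the death up to and including Day 29".
- Everyone else: "For all other participants: LOCF will be applied up to and including Day 29", with no day limit.
- After discharge: "Following discharge or early discharge LOCF will be applied to all intermediate visits". A discharge score of 3 or more becomes 2 from the next scheduled visit.

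On visits (SAP 1.4): "Study assessments will be conducted every 2 days for hospitalized participants", and the same spacing applies in follow-up. For those discharged before Day 15, a Day 15 visit is kept but "all other visits between discharge and Day 15 can be omitted". For discharge before Day 29, a Day 29 telephone visit is kept and the visits in between may likewise be left out.

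**The concern.** The definition makes one score of 6 or 7 at any time a failure. The data rules look only at scheduled scores and fill the gaps with the last one, which after discharge is at most 2. The two do not fit together. An intubation on record in the trial database, but scored at an unscheduled assessment, can be set aside while the participant is reported as having survived without ventilation. That would raise the response rate of a clinically important secondary endpoint above what the collected data show.

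**Working it through.** The SAP gives no rate, sample size or power for this endpoint, so there is no stated figure to reproduce. The check has three parts.

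**1. Which episodes are lost under the rules as written**

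| Episode | Treatment under the SAP | Result |
|---|---|---|
| Still ventilated at the next scheduled score | Observed as 6 or 7; carrying forward applies only to missing values | Failure |
| Followed by death within the window | Scored 8 at later visits | Failure |
| Starts and ends, with survival, between scheduled scores; unscheduled 6 or 7 recorded | Unscheduled score excluded by 4.2 | Success |
| As above, spanning missed or omitted visits | Missing visits filled with the earlier score | Success |

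**2. Illustrative chance that a survived episode is lost**

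Inputs from SAP 1.4: a gap *g* of 2 days in hospital; 4 days with one missed visit; 8 days for discharge on Day 7 with the next score on Day 15 (15 − 7); 14 days from Day 15 to Day 29 (29 − 15). Assumed: the intubation starts at a uniformly random point in the gap and lasts *d* days. The episode is over before the next score with probability max(0, 1 − *d*/*g*).

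| Gap *g* | *d* = 1 | *d* = 3 | *d* = 5 | *d* = 7 | *d* = 10 |
|---|---|---|---|---|---|
| 2 days | 50% | 0% | 0% | 0% | 0% |
| 4 days | 75% | 25% | 0% | 0% | 0% |
| 8 days | 87.5% | 62.5% | 37.5% | 12.5% | 0% |
| 14 days | 93% | 79% | 64% | 50% | 29% |

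With no missed visit, an in-hospital episode of 2 days or more is never lost.

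If durations are instead exponential with mean *m*, the probability is 1 − (*m*/*g*)(1 − exp(−*g*/*m*)).
- For *g* = 2: 18%, 13%, 9% and 7% at *m* = 5, 7, 10 and 14 days. For example, 1 − 2.5 × (1 − exp(−0.4)) = 0.176.
- For *g* = 14: 66%, 57%, 46% and 37% at the same means.

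The 7% to 18% in hospital comes entirely from episodes shorter than 2 days, to which an exponential distribution gives substantial weight. Under either model the post-discharge gap is the main exposure.

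These are chances per episode, given that one occurs and that no scheduled score falls inside the gap. The SAP gives no rate of intubation after discharge, so they do not convert into a number of participants.

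**3. Effect on the reported rates**

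Let *q* be the true failure proportion and *s* the share of failures lost. Recorded success is 1 − *q*(1 − *s*). With *q* = 20% and *s* from 5% to 20% (both assumed), it is 81% to 84% against a true 80%.

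For the between-arm difference, assume true failure of 20% in arm A and 30% in arm B, a true difference of 10 points:
- 10% lost in both arms: 82% − 73% = 9 points.
- 20% lost in A, 5% in B: 84% − 71.5% = 12.5 points.
- 5% lost in A, 20% in B: 81% − 76% = 5 points.

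The difference can move either way.

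**The case against.** Several counter-arguments have force.

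- **All time points may mean all scheduled time points.** That would agree with 4.2, but the SAP does not say so, and the endpoint's label would then promise more than it measures.
- **A readmitted participant is hospitalized, so 2-day scoring may resume.** Take a participant discharged on Day 7 and ventilated from Day 17 to Day 25 during a readmission. If scoring resumes, four or five scheduled scores of 6 are recorded and the participant fails. If it does not, and only unscheduled scores exist, the participant is a success. The SAP leaves both open, and the protocol, which may settle it, is not at hand.
- **Unscheduled 9-point scores may be rare.** The SAP does not say how often the scale is scored outside scheduled visits. This limits the size of the problem but does not remove the conflict.
- **Part of the list in 4.2 is redacted.** The visible text restricts it to mortality scores and refers to sections other than 6.2. Even if the ordinal scale were on the list, unscheduled data would only replace missing values, so a 6 between two observed visits would still be lost.
- **Scheduled-only ascertainment treats both arms alike.** In an open-label trial, unscheduled assessments could differ by arm. This is a real drawback of the fix, although intubation is a hard event.

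A reader might infer that every intubation between visits or after discharge becomes a success, or that the error favours the arm with more early discharges. The documents support neither. Ongoing ventilation at the next scheduled score and death within the window are still failures. The second inference needs a rate of survived post-discharge intubations, which the SAP does not give.

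**Conclusion.** The concern holds in a limited form. The definition in 6.2.1 and the exclusion in 4.2 conflict, and following both can turn a recorded intubation into a ventilator-free survival. The loss is confined to survived episodes lying wholly between scheduled scores: in hospital, those under 2 days or spanning missed visits; after discharge, potentially longer ones, if 2-day scoring does not resume on readmission.

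Both arms' rates can be too high. The number of participants affected is not stated and is probably small, and the direction of any bias in the difference is not determined. The percentages shown rest on assumed durations, random onset and assumed failure rates. The priority is minor, since the endpoint is secondary and descriptive and no test depends on it.

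**What to change.** In 4.2, add an exception for this endpoint. In 6.2.1, state that any recorded 9-point score of 6 or more on or before Day 15 (or Day 29), at a scheduled or unscheduled assessment and including during readmission, is a failure, and that carrying forward applies only where there is no such record. State also whether 2-day scoring resumes on readmission, or point to where the protocol says so. The Kaplan-Meier graph in 6.2.5 should take its ventilation date from the same records.

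The cost is SAP wording and one derivation, using scores already recorded. Response rates may be slightly lower. Because unscheduled ascertainment could differ by arm in an open-label trial, show the scheduled-visits-only result beside it as a sensitivity summary. If scheduled visits alone are what is meant, the definition should say so explicitly.
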